**D.4.2. Recruitment by race-ethnicity.** Nighttime BP differs substantially by race/ethnicity. We will not exclude people on the basis of race/ethnicity. To provide statistical power to detect differences in the validity of study results by race-ethnicity, we will recruit at least 160 white, 160 African American and 160 Hispanic participants. In a preliminary query of the I2B2 database, there were over 50,000 whites, 40,000 African Americans and 3,000 Hispanics who met the eligibility criteria at UAB in 2016. At Columbia, over 550 African Americans and 900 Hispanics have been enrolled in our recent studies of ABPM and HBPM.

**D.4.3. Recruitment by BP levels.** To ensure a broad range of clinic BP values for the current study, we will recruit 50% of our sample to have SBP  $\geq 140 \text{ mm Hg}$  or DBP  $\geq 90 \text{ mm Hg}$  based on the average of the most recent two clinic visits in their medical record.

**D.5. Screening visit.** Participants will have BP measured three times in each arm (as recommended by AHA guidelines) to determine which arm (one with higher mean BP) to use for assessing clinic BP and to confirm participants do not have orthostatic hypotension. The arm with the higher BP will be used for all BP measurements obtained during the study. For assessment of orthostatic hypotension, additional readings will be obtained after the participant has been supine for at least 5 minutes and after both 1 and 3 minutes of standing. Orthostatic hypotension will be defined as a maximum decline in SBP from supine to standing  $\geq 20 \text{ mmHg}$ . We will use the STOP-BANG Questionnaire to assess the probability of having sleep apnea. Those with a STOP-BANG score  $\geq 3$  will be considered to have a high probability of sleep apnea and excluded from enrollment.

**D.6. Study visits.** After obtaining consent, the protocol involves eight domains of data collection (Table 4). Data will be collected over one to two weeks during four study visits (Figure 3). The protocol is similar in complexity to ones we have implemented in the IDH and MHT studies and the AHA-SFRN.

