**D.11.3. Exploratory statistics comparing unattended and attended BP.** We will calculate characteristics of participants by randomization assignment: unattended then attended clinic BP measurement or attended then unattended clinic BP measurement at the first visit. Scatterplots will be assembled to show the relationship between unattended clinic BP versus awake BP and attended clinic BP versus awake BP. For each comparison, intraclass correlation coefficients will be calculated. The statistical significance of the difference in the correlation coefficients will be calculated using the Fisher r-to-z transformation accounting for the correlation between attended and unattended clinic BP. We will also assemble Bland-Altman plots showing the differences between unattended and attended BP, separately, versus awake BP on ABPM.

**D.11.4. Aim 1. Test whether measuring unattended clinic BP with an automated device will provide a more accurate estimate of awake BP on ABPM than measuring attended clinic BP with an automated device.** Our primary analyses for Hypothesis 1 will be tested using the first three clinic BP measurements obtained at Visits 1 and 2. In sensitivity analyses, we will use the fourth through sixth BP measurements from these visits. Separate analyses will be performed for SBP and DBP.

**D.11.4.1. Hypothesis 1a: The absolute difference with awake BP will be smaller for unattended vs. attended clinic BP.** The absolute difference between mean unattended clinic BP and awake BP and mean attended clinic BP and awake BP, separately, will be calculated. We will test whether these differences are statistically significantly different from zero using paired t-tests. Next, we will determine whether the absolute difference between unattended clinic BP and awake BP is smaller than the absolute difference between attended clinic BP and awake BP by calculating if the difference in differences (i.e., absolute difference between unattended clinic BP and awake BP minus the absolute difference between attended clinic BP and awake BP) is less than zero using a paired t-test. If the absolute differences between unattended and attended clinic BP and awake BP differs by randomization assignment, we will use a mixed model with randomization assignment as a covariate. This analysis will be performed in the overall population and in sub-groups defined by age (categorized in tertiles), race/ethnicity (white, African American, Hispanic) and sex.

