**D.11.5.1. Hypothesis 2a: Sleep BP on HBPM will provide an accurate estimate of sleep BP on ABPM.**

We will assemble a scatterplot of mean sleep SBP on HBPM versus ABPM and a intraclass correlation coefficient will be calculated. The statistical significance of the difference in mean sleep SBP on HBPM versus ABPM will be calculated using paired t-tests. The analysis will be repeated using sleep DBP on HBPM versus ABPM. We will create Bland-Altman plots showing the difference between sleep BP on HBPM versus ABPM by ABPM sleep BP level. We will calculate the percentage of participants who have a 10 mm Hg or larger absolute difference in their mean sleep SBP or a 5 mm Hg or larger absolute difference in their mean sleep DBP when measured by HBPM versus ABPM. Differences in mean sleep BP (SBP and DBP, separately) measured on HBPM versus ABPM will be calculated within age, race/ethnicity and sex sub-groupings. We will calculate the overall agreement and Kappa statistic between nocturnal hypertension on HBPM and ABPM, and test for a difference in prevalence using McNemar's test. We will compare differences in mean sleep SBP and DBP by randomization assignment using t-tests. If differences are statistically significant, analyses will include adjustment for randomization assignment.

**D.11.5.2. Hypothesis 2b: HBPM will be better tolerated than ABPM.** An overall score on the HBPM/ABPM tolerability questionnaire will be calculated by summing the scores on the eight Likert-type items after reverse coding positively-framed items (i.e., those with higher scores indicating better tolerability). Consistent with the approach of Viera, poor tolerance will be defined as an overall score  $\geq 75^{\text{th}}$  percentile on the results for ABPM. The cut-point identified for ABPM will be applied to define poor HBPM tolerability. Also, the percent of participants who report "pain", "skin irritation" and "bruising" from the ABPM device, and separately, the HBPM device will be calculated. The statistical significance of differences in responses to these items when wearing the HBPM and ABPM devices will be calculated using McNemar tests.

**D.11.6. Aim 3. Compare the associations of unattended versus attended clinic BP, unattended clinic BP versus awake BP on ABPM, and sleep BP on HBPM versus ABPM with two markers of end-organ damage, LVMI and ACR.**

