**D.12. Sample size/minimum detectable effects.**

[figure not shown]
**D.12.1. Aim 1.** Sample size and minimal detectable difference calculations were based on 80% statistical power and a two-sided alpha level of 5%. These calculations were performed using simulations and R version

3.3.2. We estimate that a sample size of 600 participants (630 enrolled participants with 30 participants [5%] not completing the study) will allow us to detect small but clinically relevant differences for each aim.

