#### D.12.1.1. Sample size considerations for hypothesis 1a.

**Figure 4** shows the minimal detectable difference in differences with awake ABPM comparing unattended vs attended clinic BP. With 600 participants we can detect that the absolute difference with awake ABPM is 1.5 and 1.2 mm Hg smaller for unattended vs attended clinic BP assuming a correlation of 0.5 and 0.7, respectively between clinic BP and awake BP on ABPM. In a sub-group of 160 participants (e.g., African Americans), we can detect that the absolute difference with awake ABPM is 3.1 and 2.4 mm Hg smaller for unattended vs. attended clinic BP.

Smaller absolute differences can be detected if the correlation between attended and awake BP is higher.

**D.12.1.2. Sample size considerations for hypothesis 1b.** If 85% of participants have the same concordance/discordance status for both comparisons (i.e., attended clinic hypertension versus awake hypertension and unattended clinic hypertension versus awake hypertension), enrollment of 600 participants will provide 80% statistical power to detect a difference of 5% in the two overall agreements (e.g., 70% vs. 75%). If the expected agreement is 50%, we will have an 80% statistical power to detect a difference between Kappa statistics of 0.4 and 0.5 using a two-sided alpha level of 0.05. With 600 participants and a phenotype prevalence of 15%, we can detect a difference in the prevalence of 4% when clinic BP is measured unattended versus attended. In a sub-group of 160 participants, we can detect a difference of 8%. Based on these estimates, we chose to enroll 630 participants in the proposed study (n=600 with complete data).

#### D.12.2. Aim 2

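### D.4.2 justifies 160 per race/ethnicity group as power to detect differences between groups, but D.12 gives only within-group detectable effects and no between-group contrast or interaction test is planned

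*Combined protocol and SAP*

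**What the plan says.** **Purpose of the quotas.** D.4.2 states that "we will recruit at least 160 white, 160 African American and 160 Hispanic participants", and gives the reason: "To provide statistical power to detect differences in the validity of study results by race-ethnicity". D.1 gives a similar aim for enrolling enough people in each group.

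**What is powered.** For hypothesis 1a, D.12.1.1 reads: "In a sub-group of 160 participants (e.g., African Americans), we can detect that the absolute difference with awake ABPM is 3.1 and 2.4 mm Hg", for correlations of 0.5 and 0.7. For hypothesis 2a, D.12.2.1 gives 4.0 mm Hg (SBP) and 2.7 mm Hg (DBP) as the mean HBPM-ABPM differences that one sub-group of 160 can exclude. The remaining n=160 figures (prevalence in D.12.1.2, correlations in Table 7) also concern one sub-group.

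**What is analysed.** D.11.4.1, on hypothesis 1a: "This analysis will be performed in the overall population and in sub-groups defined by age", then race/ethnicity and sex. D.11.5.1 says that mean sleep-BP differences "will be calculated within age, race/ethnicity and sex sub-groupings". D.16 calls the stratified analyses exploratory, and E.1.6.2 speaks of analysing the three groups separately. D.11.2 uses race/ethnicity only as an adjustment covariate. The Statistical analysis section of the Analysis Plan has no race/ethnicity sub-group analysis.

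**The concern.** Whether a BP method's validity differs by race/ethnicity is a question about the difference between two group-specific effects. A separate analysis in each group estimates each effect but not how far apart they are. One group can show a significant result and another not while the two estimates are compatible, particularly when group sizes differ. The contrast is also less precise than either estimate: with equal groups its standard error is √2 times the one-group standard error.

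A reader who takes D.4.2 together with the n=160 figures in D.12 could conclude that the study can detect between-group differences of the sizes listed there. At stake is a stated reason for the recruitment quotas, and the interpretation of any later statement that a method works equally or unequally well across groups. The overall-population tests of the hypotheses are not affected.

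**Working it through.** **Inputs.** Two-sided 5% and 80% power (D.12.1); 160 per group (D.4.2); 1a figures of 1.5/1.2 mm Hg at n=600 and 3.1/2.4 at n=160 (D.12.1.1); 2a SDs of 15 (SBP) and 10 (DBP), correlation 0.5, and 4.0/2.7 mm Hg at n=160 (D.12.2.1); 210 non-Hispanic Black, 210 non-Hispanic White and 210 Hispanic participants (PHS Inclusion Enrollment Report).

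**Step 1: the plan's own one-group figures.** One-group detectable difference = (1.960 + 0.842) × SD/√n = 2.802 × SD/√n.

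- *1a.* The text gives no SD, so only scaling can be checked. 1.5 × √(600/160) = 2.90 against 3.1 stated; 1.2 × √(600/160) = 2.32 against 2.4. The implied SD of the paired quantity is 3.1 × √160/2.802 = 14.0 or 1.5 × √600/2.802 = 13.1 (r = 0.5), and 10.8 or 10.5 (r = 0.7). Both versions are carried forward.
- *2a.* SD of the paired difference = √(15² + 15² − 2 × 0.5 × 15 × 15) = 15 for SBP, and likewise 10 for DBP. At n=160 the SBP figure is 2.802 × 15/√160 = 3.32 (two-sided paired test), or 3.47 and 3.84 for equivalence with two one-sided tests at 5% and 2.5%. The stated 4.0 is not reproduced by any of these and is conservative.

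**Step 2: two groups of 160.** SE = SD × √(2/160) = 0.1118 × SD. Power = Φ(gap/SE − 1.960). Detectable gap = 2.802 × SE.

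| Hypothesis, assumed gap | SD | SE | Power | Gap detectable with 80% power |
|---|---|---|---|---|
| 1a, 3.1 mm Hg | 14.0 | 1.565 | Φ(1.98 − 1.96) = 51% | 4.4 mm Hg |
| 1a, 3.1 mm Hg | 13.1 | 1.466 | 56% | 4.1 mm Hg |
| 1a, 2.4 mm Hg | 10.8 | 1.21 | 51% | 3.4 mm Hg |
| 1a, 2.4 mm Hg | 10.5 | 1.17 | 53% | 3.3 mm Hg |
| 2a SBP, 4.0 mm Hg | 15 | 1.677 | Φ(2.385 − 1.96) = 66% | 4.7 mm Hg |
| 2a DBP, 2.7 mm Hg | 10 | 1.118 | Φ(2.415 − 1.96) = 68% | 3.1 mm Hg |

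The 51% is what any design gives when the gap equals a one-group difference detectable with exactly 80% power: Φ(2.802/√2 − 1.960) = 0.508. The 2a rows are higher because the stated 4.0 and 2.7 exceed the exact one-group values.

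**Step 3: planned enrolment of 210 per group.** For 2a SBP, 4.0/(15 × √(2/210)) = 2.73, so power is Φ(0.77) = 78%. For DBP, 2.7/(10 × √(2/210)) = 2.77, giving 79%. With the planned 5% loss (about 200 per group) these become 76% and 77%. For a gap equal to the exact one-group detectable difference at n=160, power is Φ(2.802 × √(210/160)/√2 − 1.960) = 62%.

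**Step 4: multiplicity.** With Bonferroni over the three pairwise contrasts, the 51% becomes Φ(2.802/√2 − 2.394) = 34%.

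**The case against.** The best defence is that the sub-group work is modest in intent. D.16 labels it exploratory, none of hypotheses 1a to 3c concerns race/ethnicity, and 160 is a minimum. At the planned 210 per group, the sleep-BP contrast at the stated values is close to 80%, and sleep BP is the aim closest to D.4.2, which opens with night-time BP. This stands: it limits the point to exploratory analyses and makes the shortfall for 2a small at planned enrolment. It does not supply the missing contrast, and D.4.2 still sets quotas by a power statement that nothing in D.12 supports.

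A reader might infer that the plan claims 80% power for differences between groups and really has 51%. The documents do not support that. They attach 80% only to within-group effects and name no between-group effect size, so power for D.4.2's purpose is undefined until a gap is assumed. A reader might also infer that the investigators would declare group differences from within-group p-values. The text does not say so; it plans separate estimates and is silent on how groups would be compared.

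A further objection is that the Analysis Plan's Table 1 already reports 291 non-Hispanic White, 132 non-Hispanic Black and 39 Hispanic participants, so calculations at 160 or 210 per group describe the design and not the enrolled sample. That is correct. It is also a reason to report contrasts with intervals, because separate results in groups of such unequal size are hard to compare.

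**Conclusion.** The point holds as a mismatch between the stated purpose and both the power calculation and the analysis. D.4.2 promises power for differences by race/ethnicity. D.12 provides only within-group figures, and neither D.11 nor the Analysis Plan contains a between-group contrast or interaction test.

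The size depends on the gap assumed. At 160 v 160 it is about 51% power at the 1a one-group figures (up to 56% with the SD implied by the n=600 figures) and about 66-68% at the stated 2a values, with 78-79% for 2a at 210 per group. These figures assume equal groups, equal SDs, a normal approximation and no multiplicity adjustment. They also assume that the one-group figures are sensible between-group gaps. For 2a that is a convenience, since 4.0 and 2.7 are stated as differences to be excluded.

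D.4.2 makes no power claim for sex or age, so extending the criticism of the power statement to those sub-groups would go too far.

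**What to change.** 1. For 1a and 2a, compute each participant's paired difference (unattended minus attended absolute error; HBPM minus ABPM) and regress it on race/ethnicity. Because the outcome is already a difference between methods, the race/ethnicity effect is the method-by-group interaction. Report the group contrasts with 95% confidence intervals and the interaction p-value, labelled exploratory and added after the plan. Present within-group estimates descriptively. The same model can be used for sex and age group.
2. In D.12, label the n=160 figures as within-group.
3. Either add the between-group detectable differences (at 160 per group, about 4.1-4.4/3.3-3.4 mm Hg for 1a and 4.7/3.1 mm Hg for 2a), or reword D.4.2 so that the quotas are justified by precision within each group.

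The cost is wording and one simple model per outcome on data already collected. The downside is that the stated sub-group power becomes less favourable.

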**Table 4. Domains of data collection**

1. Unattended clinic BP
2. Attended clinic BP
3. 24-hour ABPM with actigraphy
4. One night of HBPM with actigraphy
5. Questionnaires including HBPM and ABPM tolerability
6. A brief physical examination
7. Spot urine to assess albuminuria
8. Transthoracic echocardiogram

ABPM monitor and actigraph removed. Data will be downloaded onto computers dedicated to the current study. The ABPM recording will be checked for completeness. If a complete recording is not obtained, participants will be asked to repeat the ABPM procedure. Once a complete ABPM is confirmed, participants will fill out the ABPM tolerability questionnaire (**Section D.8.5**). This questionnaire will be self-administered unless participants are unable to read, in which case, it will be interviewer administered. Participants will be given an HBPM device and instructed in its use as described in **Section D.8.4.3**.

**D.6.3.2. Participants randomized to undergo HBPM then ABPM.** At Study Visit 3, participants will return the HBPM device and have the actigraph removed. Data will be downloaded onto computers dedicated to the current study and the recording will be checked for completeness. Next, participants will be asked to fill out a questionnaire on the tolerability of HBPM (**Section D.8.5**). This questionnaire will be self-administered unless participants are unable to read, in which case, it will be interviewer administered. Participants will be fitted with an ABPM device and instructed in its use as described in **Section D.8.4.2**.

**D.6.4. Study Visit 4.** Identical activities will occur at Study Visits 3 and 4 (i.e., the ABPM or HBPM devices will be returned, checked for a complete recording, and a tolerability questionnaire will be filled out). At the conclusion of Study Visit 4, participants will be escorted by study staff to the laboratory for an echocardiogram. Upon completion of the echocardiogram, participants will have successfully completed the study.

Figure 3. Activities conducted at a screening visit and the four study visits.

Screening visit	Visit 1	Visit 2	Visit 3	Visit 4

 
Informed consent
 
BP measurement in both arms
 
Sleep apnea screener
 
Orthostatic hypotension assessment
 
Questionnaires
 
	
 
Informed consent
 
Randomization 1
 
Clinic BP measurements (attended then unattended or unattended then attended)
 
Brief physical exam
 
Questionnaires
 
	
 
Clinic BP measurements (attended then unattended or unattended then attended)†
 
Randomization 2
 
Initiate ABPM or provide instructions for HBPM sleep assessment
 
 
† Order will be opposite of Visit 1
	
 
Return equipment for ABPM or HBPM
 
Check completeness of readings
 
Tolerability questionnaire
 
Initiate alternate procedure (ABPM or HBPM)
 
	
 
Return equipment
 
Check completeness of readings
 
Tolerability questionnaire
 
Echocardiogram
 

**D.7. Randomization.** Each participant will be randomized two times in the current study. At Study Visit 1, we will randomize participants to have their clinic BP measured either unattended and then attended or attended and then unattended. After the assessment of clinic BP at Study Visit 2, participants will be randomized to complete ABPM then HBPM or HBPM then ABPM. Each randomization will be separate and independent. Randomization will be performed by site (i.e., UAB and Columbia University) and we will use block sizes of 2, 4, or 8. Randomization assignments will be generated by a statistician at UAB using SAS Version 9.4 and stored in a RedCap database created and maintained by a programmer at UAB (**Section D.10.1**).

**D.8. Measures.** A brief examination will occur at the end of Study Visit 1. This exam will include anthropometrics, fasting blood and urine collection, and completion of questionnaires.

**D.8.1. Anthropometric measures.** With participants wearing a gown provided by the study, a calibrated scale will be used to measure weight. Height will be measured with the participants' shoes off using a metal centimeter tape-measure. A flexible tape measure will be used to measure waist circumference midway between the lowest ribs and the iliac crest and neck circumference at the level of the cricothyroid membrane.

**D.8.2. Blood and urine measurements.** A fasting blood draw will be performed by a research coordinator with phlebotomist training, and participants will also be asked to provide an untimed (spot) urine sample. Total and HDL cholesterol, triglycerides, serum creatinine, hemoglobin A1c, and glucose will be assayed. Serum creatinine will be measured using an IDMS-traceable approach. eGFR will be estimated using the CKD-EPI equation. *Urinary albumin and creatinine will be measured using nephelometry.*

**D.8.3. Questionnaires.** Questionnaires will be self-administered. English and Spanish versions of the questionnaires will be used. For participants who cannot read, questionnaires will be interview administered.

**D.8.3.1. Sociodemographic factors and medical history.** Age, race/ethnicity, sex, household income, education, medical history (e.g., history of diabetes) and medication use will be determined by questionnaires. We will adapt questionnaires from our prior NIH- and AHA-SFRN funded studies for administration.

**D.8.3.2. Psychosocial factors.** Depressive symptoms will be assessed using the 20-item Centers for Epidemiologic Studies of Depression (CES-D); discrimination by a questionnaire used in the Coronary Artery Risk Development in Young Adults (CARDIA) study; perceived stress by the Perceived Stress Scale; and trait anxiety by the State-Trait Anxiety Inventory –Trait Scale (TAI). These scales are written at less than the 8th grade level, should take 20 minutes to complete and have been validated in multi-ethnic populations.

**D.8.3.3. Sleep duration and quality.** Sleep duration and quality will be assessed using the Pittsburgh Sleep Quality Index (PSQI), a validated instrument that provides a measure of global sleep quality and sleep duration over the previous month.

**D.8.3.4. Seasonal temperature.** High and low outdoor temperatures will be recorded using National Oceanic

*and Atmospheric Administration data for the ABPM and home sleep BP monitoring periods. We will use these data to investigate whether temperature affects the association of unattended versus attended clinic BP with ABPM and the correlation of sleep BP on ABPM compared with HBPM. The temperature of the room where clinic BP is measured will be kept at 72 degrees and checked prior to each participant's clinic visits.*

